**c) Number of Subjects**

**Activity 1:** Estimated sample size of 51,000 patients.

**Activity 2:** 20-40 participants in year 5.

**Activity 3:** Approximately 10-30 participants (HH leadership and CMA leadership, care managers).

**Activity 4:** Estimated sample size of 60,000 patients

**d) Study Timelines**

**Activity 1:** This is a retrospective cohort analysis. We will examine two data sets: one with data from 2007-2014, and one with data from 2010-2017. The project has been funded from 3/1/2016-2/28/2021.

**Activity 2:** We completed our year 2 focus groups and interviews by 8/31/2018 and we anticipate completing year 5 focus groups by 2/2021. Participation in the study will consist of being a part of an interview, and optional follow up activities (receiving study results). The project has been funded from 3/1/2016-2/28/2021.

**Activity 3:** We completed our first round of HH leadership interviews by 8/31/18. Year 5 interviews will be conducted by 2/2021. The project has been funded from 3/1/2016-2/28/2021.

**Activity 4:** We anticipated conducting primary analyses by 6/30/2021.

**e) Variable and endpoints**

**Activity 1 and 4:** For this aspect of the study, we will examine multiple endpoints related to process of care, outcomes, and racial/ethnic disparities. We will examine variable and endpoints in the following categories:

**1) Individual level characteristics**

Variables include gender, age, race/ethnicity, health insurance type, health care site, patient zip code, and tobacco use.

**2) Health home indicators and patient co-morbidities**

Indicators available include whether the individual was enrolled in the HH program, the date of joining the program, the name/location of the HH, patient-level co-morbidities and chronic conditions (additional diagnoses).

### 3) Process measures

In consultation with the Diabetes Subcommittee of the NYC-CDRN, the following process measures have been identified (see Table 2). Several organizations in the United States have developed sets of quality metrics that can be used to evaluate the adequacy and appropriateness of processes of care and outcomes for patients with diabetes. These include the Centers for Medicare and Medicaid Services (CMS), the Pharmacy Quality Alliance (PQA), the National Committee for Quality Assurance (NCQA)'s Healthcare Effectiveness Data and Information Set (HEDIS), and the Agency for Healthcare Research and Quality's (AHRQ) Prevention Quality Indicators (PQI) (which assess the quality of care for "ambulatory care sensitive conditions," also known as preventable admissions).(30-33)

Table 2. Process Measures	
Metric	Component
Adherence to Chronic Medications (CMS)	At least two prescriptions for statins and a Proportion of Days Covered (PDC) of at least 0.8 during the measurement period (12 consecutive months)
Adherence to Chronic Medications (CMS)	At least two prescriptions for ACEIs/ARBs and a PDC of at least 0.8 during the measurement period (12 consecutive months).
Adherence to Chronic Medications (CMS)	At least two prescriptions for a single oral hypoglycemic agent or at least two prescriptions for multiple agents within an antidiabetic class and a PDC of at least 0.8 for at least 1 antidiabetic class during the measurement period (12 consecutive months).
Eye Exam (NCQA)	Received a retinal or dilated eye exam during the measurement year or a negative retinal or dilated eye exam in the year prior to the measurement year.
HbA1c testing (NCQA)	Received an HbA1c test during the measurement year.
LDL-C Screening (NCQA)	Received an LDL-C test during the measurement year.
Medical Attention for Nephropathy (NCQA)	Received a nephropathy screening test or had evidence of nephropathy during the measurement year.
Appropriate Treatment of Hypertension (PQA)	If dispensed a medication for diabetes and hypertension, are receiving an angiotensin-converting -enzyme-inhibitor (ACEI) or angiotensin receptor blocker (ARB) or direct renin inhibitor (DRI) renin-angiotensin-antagonist medication.
Foot exam (NCQA)	Received a foot exam (visual inspection with either a sensory exam or a pulse exam) during the measurement year.

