Similar care management programs have been shown, in studies of limited scope, to improve intermediate outcomes for patients with diabetes. However, the impact of HHs on processes of care and outcomes among low-income patients with diabetes mellitus in large, diverse, and complex urban settings remains largely unexplored. Additionally, current research on the impact of HHs, both in NYS and elsewhere, does not incorporate individual-level clinical data on chronic disease management. As a result, whether the Medicaid HHs program has impacted the health of patients with diabetes has not been examined. It is also not known how interventions of this scope will affect long-standing racial and ethnic disparities in the quality of care and outcomes of individuals with diabetes. Since similar programs are being implemented nationally, it now is critically important to evaluate the effects of HHs on the process and outcomes among patients with diabetes, a condition with multiple complications, which are disproportionately prevalent among racial and ethnic minorities and low-income populations in the United States.

We plan to use two complementary sources of longitudinal individual-level data: 1) NYS Medicaid administrative and claims data and 2) the New York City-Clinical Data Research Network (NYC-CDRN), funded by the Patient-Centered Outcomes Research Institute (PCORI). The NYC-CDRN has identified a cohort of patients with diabetes (approximately 90,700 Medicaid enrollees with diabetes) from 7 large health systems based on electronic health record data; and it has developed a common data model that includes clinical variables related to the process and outcomes of care of patients with diabetes. Using information available from the two complementary data sources and quasi-experimental methods, we will assess the impact of Medicaid HHs in NYC.

Among adult Medicaid patients with diabetes in NYC, we propose:

**Aim 1:** To assess the impact of HHs on the process of care for patients with diabetes.

**Aim 2:** To assess the impact of HHs on the health outcomes of patients with diabetes.

**Aim 3:** To assess the impact of HHs on racial and ethnic disparities in the process of care and outcomes among Medicaid patients with diabetes.

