Our sample will include Medicaid enrollees with diabetes who are seen at NYC-CDRN sites and in HHs (estimated 6,500-20,000) and a matched comparison group of Medicaid enrollees with diabetes who are part of the NYC-CDRN, but not HHs. We plan to develop a set of propensity score matched controls, based on a set of patient, practice, and market-level (zip-code) characteristics. We will use quasi-experimental methods to investigate the magnitude of the effects of the HHs program between 2010 and 2017. This secondary data analysis is referred to as **Activity 1** in this protocol. In addition, we will gather information regarding the patient experience of HHs through interviews (**Activity 2**). We will also utilize interviews with HH leaders and care managers from NYC HHs to further characterize these entities (**Activity 3**). Columbia University will participate in only **Activity 1**.

8/20/20 update: Apart from evaluating the impact of the NYS Medicaid HH program on the process and outcomes of care for low-income NYC residents with diabetes, compared to non-enrolled residents with similar conditions and utilization histories, we have received funding to extend this work to examine the impacts of the COVID-19 pandemic on this vulnerable population, a majority of which is Black or Latinx. We hypothesize that HH participation will reduce pandemic-related disruptions in access to health care and social services and improve health outcomes among patients with diabetes in NYC. Using a quasi-experimental difference-in-differences design, we will contrast access and utilization of health care and social services and health outcomes among HH enrollees and non-enrollees during a baseline period prior to the pandemic (CY2019) with each month of the pandemic time period (2020).

**Aim 4:** Using Medicaid claims data, we will estimate the impact of HH enrollment compared to usual care among Medicaid-insured patients with diabetes and other chronic conditions on access to health care and social services and COVID-19 and non-COVID-19 clinical outcomes, as well as racial/ethnic disparities in these outcomes, before and during the pandemic in NYC.

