### 4) Outcome measures

In consultation with the Diabetes Subcommittee of the NYC-CDRN, the following outcome measures have been identified (see table below). As with the identified process measures, these are metrics identified and developed by major quality reporting organizations, which means that results will be readily interpretable by policymakers and easily compared to other studies and datasets.(30)

In order to assess these metrics, and to perform individual-level longitudinal analyses, we will evaluate health system utilization and intermediate and long term outcomes. Outcomes will include:

- 1) Intermediate outcomes:HbA1c, blood pressure, LDL and renal function
- 2) Long-term outcomes: we will use validated ICD-9 code based-algorithms to assess
  - a. macrovascular outcomes (stroke and myocardial infarction)
  - b. microvascular outcomes (nephropathy, end-stage renal disease, neuropathy, amputation, retinopathy, and blindness)
- 3) Utilization outcomes:
  - a. Number and diagnoses associated with diabetes-related preventable hospitalizations
    - i. uncontrolled diabetes admissions
    - ii. diabetes short-term complications admissions (diabetic ketoacidosis, hyperosmolarity, coma)
    - iii. and long-term complications admissions (renal, eye, neurological, and circulatory disorders)
  - b. ER visits
  - c. Outpatient visits.

Table 3. Outcome measures	
Metric	
HbA1c Control (<8.0%) (NCQA)	
HbA1c Poor Control (>9.0%) (NCQA)	
Blood Pressure Control (<140/90 mm Hg) (NCQA)	
Uncontrolled Diabetes Admissions Rate (PQI 14) (AHRQ)	
Diabetes Short-Term Complications Admissions (PQI 1) (AHRQ)	
Diabetes Long-Term Complications Admissions (PQI 3) (AHRQ)	
Lower-Extremity Amputation Among Patients With Diabetes (PQI 16) (AHRQ)	
Medical Attention for Nephropathy (NCQA)	

**Activity 2:** For this qualitative research, we will identify cross-cutting themes from interviews.

**Activity 3:** Data collected through these interviews will be utilized to categorize HH, CMA, and care manager activities and experiences.

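### The nephropathy process measure counts having the complication as care delivered, so it mixes kidney screening with disease prevalence

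*Protocol*

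**What the plan says.** Aim 1 in the Protocol's Objectives is "To assess the impact of HHs on the process of care for patients with diabetes"; Aim 3 asks how HHs affect racial and ethnic disparities in process and outcomes. Section 5e, 3) Process measures, presents the published quality metrics as tools to "evaluate the adequacy and appropriateness of processes of care and outcomes for patients with diabetes" and lists nine rows in Table 2. The nephropathy row, credited to NCQA, is met if the patient "Received a nephropathy screening test or had evidence of nephropathy during the measurement year".

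Section 5e, 4) Outcome measures, lists nephropathy among the long-term harms: "microvascular outcomes (nephropathy, end-stage renal disease, neuropathy, amputation, retinopathy, and blindness". Table 3 then repeats Medical Attention for Nephropathy as an outcome metric, with no separate definition. The same section explains why published metrics were chosen, for process and outcome measures alike: "which means that results will be readily interpretable by policymakers and easily compared to other studies and datasets".

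The Protocol does not say that the test component will be reported separately. It gives no screening rate and no nephropathy rate.

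**The concern.** The other Table 2 rows are met only by care or treatment: a test, an exam, or medication received. Even the eye row, which accepts the previous year, requires an exam with a negative result. Only the nephropathy row can be met by having the complication.

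Take three patients, none tested in the year. One has long-standing nephropathy recorded again, one has new nephropathy, and one has none. The first two score as met and the third as not met, although all three received the same screening. The second patient is also a microvascular event under Aim 2, so one finding counts as success in one aim and harm in another.

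What is at stake is interpretation. A difference in this score cannot be read as a difference in kidney screening unless prevalence is known to be equal and stable, and even then the absolute effect is understated.

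**Working it through.** The Protocol has no figure to reproduce. The scoring rule comes from Table 2; all rates below are assumptions.

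**Formula.** Let p be the share with evidence of nephropathy in the year and s the testing rate among the rest. Score = p + (1 - p)s, and the failure share = (1 - p)(1 - s).

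**1. Equal p in both arms: dilution only.** The score difference is (1 - p) times the screening gain.
- Gain of 10 points (s from 60% to 70%): 8, 7 or 6 points at p = 20, 30 or 40%.
- Gain of 5 points (s from 70% to 75%): 4.5, 4.0, 3.5 or 3.0 points at p = 10, 20, 30 or 40%.
- On the odds-ratio scale the loss is small. The 5-point gain has odds ratio (0.75/0.25)/(0.70/0.30) = 1.286. At p = 40% the scores are 82% and 85%, giving (0.85/0.15)/(0.82/0.18) = 1.244.

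**2. p changes, s does not: bias in either direction.**
- HH lowers p from 30% to 27%: change = -0.03(1 - s), or -1.5, -1.2 and -0.9 points at s = 50, 60 and 70%.
- HH raises recorded nephropathy from 20% to 25% at s = 70%: 77.5% - 76.0% = +1.5 points, a false benefit.

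**3. When the sign reverses.** This needs (1 - p_HH)(1 - s_HH) > (1 - p_C)(1 - s_C) although s_HH > s_C. With controls at p = 30% and s = 70%, the control failure share is 0.7 × 0.3 = 0.21.
- Gain of 1 point: 0.21/0.29 = 0.724, so p_HH must be more than 2.4 points lower.
- Gain of 2 points: 0.21/0.28 = 0.75, more than 5.0 points lower.
- Gain of 5 points: 0.21/0.25 = 0.84, more than 14 points lower.
- Example: p = 25%, s = 71% in HH gives 78.25% against 79.00%, a difference of -0.75 points.
- With controls at s = 90% and p = 30% (failure share 0.07), a 2-point gain needs a drop of more than 17.5 points. A 5-point gain cannot be reversed, since 0.07/0.05 exceeds 1.

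**4. Difference-in-differences, p unequal but stable.** With a secular change c in s common to both arms and true gain d, the estimate is (1 - p_HH)d - (p_HH - p_C)c. At p_HH = 30%, p_C = 20% and c = 10 points it is 0.7d - 1 point, negative only if d is below 1.4 points.

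**5. Racial/ethnic groups.** At s = 60% in both groups, p = 40% scores 0.40 + 0.60 × 0.60 = 76% and p = 30% scores 0.30 + 0.70 × 0.60 = 72%: a 4-point gap with equal screening. An identical 10-point HH gain shows as 6 and 7 points.

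**The case against.** The strongest reply is that this is a named quality metric, not a screening rate. It was chosen for a stated reason, and Aim 1 concerns process of care in general. That stands: using the composite is not an error in the plan, and it should be kept. But comparability with other studies does not make the composite answer whether patients were screened, and the Protocol itself fixes the numerator.

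A reader might infer that the measure will reverse the sign of the HH effect, or always works against HHs. The documents support neither. Equal prevalence gives dilution only; reversal needs the gaps in step 3, and no rates show that they exist. More recorded nephropathy under HHs would inflate the score. The plan also uses controls matched on characteristics of patients, practices and areas, which should limit baseline differences between arms. Matching does not fix later changes in prevalence, and it is not described as balancing racial/ethnic groups against one another.

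Other points against also hold:
- Power is not threatened. With 6,500 per arm, the lower end of the estimate for patients "in HHs (estimated 6,500-20,000", and clustering and matching ignored, power for a 5-point gain stays at or above 98% for s of 60 to 90% and p up to 40%.
- A stable 4-point gap in level between racial/ethnic groups is not in itself an HH effect, which is what Aim 3 asks about. Unequal dilution (6 against 7 points) and any change in prevalence remain.
- The Protocol does not define what counts as evidence of nephropathy. How often it occurs without a test is unknown.
- Excluding nephropathy before each patient's own entry date would not work well. Controls have no defined entry date, and the exclusion would remove cases from the pre-period but not the post-period.

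**Conclusion.** The concern holds as a limit on what the composite can show. The row credits the complication as care, and the score combines screening with prevalence. With equal prevalence, 60 to 90% of an absolute screening effect is retained for p between 40% and 10%. With unequal or changing prevalence the bias can go either way, about 1 to 1.5 points in the step 2 examples. Aim 3 is the more exposed aim, because the Background section on diabetes complications names renal disease among complications that add to disparities, so unequal prevalence between groups is part of the Protocol's own premise. Sign reversal is a conditional possibility, not a finding. All sizes rest on assumed rates. The improvement is worthwhile because it is cheap. A statistical analysis plan, not available here, may already report the test component.

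**What to change.** Keep the NCQA composite and report it for comparability. For Aims 1 and 3, add one endpoint: receipt of a nephropathy screening test in the measurement year, with a diagnosis alone not counting as met. Restrict it to patients with no evidence of nephropathy before one common baseline, the start of the first pre-period measurement year. Apply that restriction identically to HH and comparison patients and to the pre and post periods. State that any conclusion on kidney screening rests on this endpoint.

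The cost is one line in Table 2 and one variable derived from the merged claims and EHR data, with some data before the baseline kept as look-back. The denominator for this endpoint falls, to 60 to 80% of the cohort if 20 to 40% have prior nephropathy (an assumption). The component is not the strict NCQA metric, which is why the composite stays beside it.

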### **Medicaid Health Homes and Diabetes Management**

HH-eligible patients with diabetes are likely to be an especially vulnerable population, and one where disparities in access and quality are starker. The prevalence of diabetes among patients with serious

mental illness (SMI) is higher than in the general population. Increased mortality among those with SMI is partially attributable to higher rates of cardio-metabolic disease.(23, 24) Patients with SMI and diabetes have been found to be less likely to receive indicated services and care, and more likely to be admitted to the hospital with ambulatory-care sensitive conditions when compared to those without SMI.(23, 25) Over half of patients with diabetes have at least one other chronic condition, and a large proportion of these have two or more.(26, 27) Suffering from multiple chronic diseases puts individuals at greater risk of preventable hospitalizations, poor functional status, higher cost care, and increased mortality.(26, 28)

HH enrollment would ideally improve the processes and the outcomes of care; and it would reduce health disparities (related to the process and outcomes of care) for individuals with diabetes. Through coordination of care, intensive case management, and attention to social needs, individuals with diabetes could develop better disease self-management, receive proper specialist evaluation and evidence-based regimens, and work with a team that identifies opportunities to bolster social support. As the HH intervention is applied differently at different facilities, these effects may vary across institutions. In NYS, evaluations are currently being conducted of the overall HHs program and of those participants with substance use disorders and those with HIV; however, by focusing on individuals with diabetes, the proposed research would add substantially to knowledge about the effect of HHs on patients on an important common chronic condition, diabetes.

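### The hypertension process measure is scored only among patients dispensed treatment, which Health Homes may change, so the estimated effect can move either way through who enters the denominator

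*Protocol*

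**What the plan says.** Aim 1 in section 1 of the protocol is "To assess the impact of HHs on the process of care for patients with diabetes". Table 2 in section 5e lists nine process measures for it, and four of them concern drugs.

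- **Appropriate Treatment of Hypertension (PQA).** The row opens "If dispensed a medication for diabetes and hypertension, are receiving" and then names ACE inhibitors, ARBs and direct renin inhibitors. It is an if-then rule: dispensing decides who is scored. The row gives no measurement period and no baseline anchor.
- **Adherence to Chronic Medications (CMS), three rows.** The ACEI/ARB row reads "At least two prescriptions for ACEIs/ARBs and a PDC of at least 0.8 during the measurement period (12 consecutive months". The statin row has the same form. The oral hypoglycemic row also asks for at least two prescriptions and "a PDC of at least 0.8 for at least 1 antidiabetic class during the measurement period (12 consecutive months". None of the three names a denominator.

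The Background subsection on Medicaid Health Homes and Diabetes Management expects that patients in HH could "receive proper specialist evaluation and evidence-based regimens". Comparators are to be propensity score matched on patient, practice and zip-code characteristics (section 1).

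**The concern.** The hypertension measure conditions the comparison on an event that HH may itself cause. A patient who is not dispensed these drugs is not scored. If HH brings that patient onto treatment, the patient enters the HH denominator, while a similar untreated comparator stays out. The two groups are then no longer the matched groups. They are the treated parts of those groups, selected after HH began. Matching balances characteristics at baseline and does not balance who is dispensed a drug later.

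An effect estimate from this measure therefore mixes two things: a change in prescribing among patients who would have been treated anyway, and a change in who is treated. A programme that starts treatment in previously untreated patients could score lower, higher or the same. Aim 3 inherits the problem: if HH starts more untreated patients in one racial or ethnic group than in another, the score could suggest a change in disparity that comes only from the denominator. Table 2 has no measure of starting treatment that would show this.

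**Working it through.** The protocol gives no expected rate, power or effect size for these measures, so there is no planned figure to reproduce. The check is a mixture identity with assumed inputs, shown over a range.

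**Notation.** N = all patients in a group; n0 = patients treated with or without HH; p0 = their pass rate; m = patients newly treated because of HH; q = their pass rate. HH is assumed not to change p0, so any movement comes from the denominator alone.

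- Score among those dispensed: S = (n0·p0 + m·q) / (n0 + m)
- Change in score: S − p0 = m·(q − p0) / (n0 + m), which is negative exactly when q < p0
- Share of all patients passing: A = (n0·p0 + m·q) / N, which rises for any q above 0

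**Hypertension measure.** Assumed: N = 1,000, n0 = 600, p0 = 80% (480 passing), m = 100. Without HH, S = 80.0% and A = 48.0%.

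| q | S with HH | Change in S | A with HH |
|---|---|---|---|
| 50% | 530/700 = 75.7% | -4.3 points | 53.0% |
| 60% | 540/700 = 77.1% | -2.9 points | 54.0% |
| 80% | 560/700 = 80.0% | 0 | 56.0% |
| 90% | 570/700 = 81.4% | +1.4 points | 57.0% |

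With m = 50 the change runs from -2.3 (q = 50%) to +0.8 points (q = 90%). With m = 150 it runs from -6.0 to +2.0 points.

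**Would it show?** The lower end of the protocol's estimate for the HH group is 6,500 (section 1). Assume 6,500 comparators, with 60% treated there (3,900) and 70% in HH (4,550). For 80.0% against 77.1%:

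- SE = √(0.80×0.20/3,900 + 0.7714×0.2286/4,550) = 0.0089
- z = 0.0286/0.0089 = 3.2
- probability of significance at an assumed two-sided 5% = Φ(3.2 − 1.96), about 89%

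This treats the samples as independent and ignores clustering, so it indicates scale only.

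**Adherence measures, two readings.**

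1. Two prescriptions is the entry condition. Assume 600 users, 65% with proportion of days covered (PDC) of at least 0.8 (390), and 100 new users. The score is 420/700 = 60.0% (-5.0 points) at q = 30%, 430/700 = 61.4% (-3.6) at 40%, unchanged at 65%, and 465/700 = 66.4% (+1.4) at 75%. The share of all patients rises from 39.0% to 42.0%, 43.0%, 45.5% and 46.5%.
2. Two prescriptions is part of the criterion, scored in all patients. An untreated patient fails, and a new adherent user counts as a gain. The denominator effect is zero.

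**The case against.** The strongest reply has four parts.

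*A reader might infer that four of the nine process measures are affected.* The text does not support that. The adherence rows join two prescriptions and the PDC threshold with the word and, in a column headed Component. Read literally, both are things to be achieved. In favour of the other reading, days covered mean little for a patient never prescribed the drug, and two prescriptions add little once a PDC of 0.8 over 12 months is required. The document does not settle it, so the claim is firm for one measure and conditional for three.

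*A reader might also infer that the bias always runs against HH.* It does not. If HH moves patients onto evidence-based regimens, the newly started patients could receive a listed agent as often as existing patients or more often. The direction is open. What stands is that the groups are compared on different, treatment-selected subsets.

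*Nor is it right that a null or negative result could never be told apart from success in starting treatment.* Table 3 includes HbA1c control and blood pressure control, neither of which is conditioned on dispensing, and the merged claims and EHR data allow treatment starts to be examined.

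*Standard metrics are a deliberate choice, and denominators belong in an analysis plan.* Section 5e (Outcome measures) values metrics that policymakers can interpret and compare. That is a good reason to report the standard rate, but it does not make the rate an unbiased basis for an effect estimate. An analysis plan could well supply denominators that the protocol leaves open, as in the adherence rows. The hypertension row is different, because the protocol states its condition. That row gives no period, so if the condition were read in the baseline period the problem would not arise. The row does not say so.

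**Conclusion.** The point holds for the Appropriate Treatment of Hypertension measure. As written, it makes scoring depend on dispensing with no pre-enrolment anchor, while the protocol expects HH to influence treatment. In the assumed scenarios the score shifts by between -6.0 and +2.0 points with no change in prescribing among patients already treated, and the share of all patients on a listed agent rises throughout. At the protocol's own HH group size, a shift of about 3 points could well be reported as a real difference.

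This rests on two conditions: dispensing is assessed over the period being scored, and HH changes who is treated. The rates are assumptions chosen to show the mechanism and do not predict this study's results. For the three adherence measures the conclusion is conditional: the same problem exists if two prescriptions is the entry condition, and none exists if it is part of a criterion scored in all patients.

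**What to change.** For the HH effect estimates based on Table 2:

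- **Hypertension measure.** Set eligibility (diabetes and hypertension drugs dispensed) in the pre-index baseline period in both groups, with an index date assigned to comparators. Keep those patients in the denominator whatever they fill later. Also report the proportion of all matched patients meeting the numerator, so that new starters count as gains.
- **Adherence measures.** State whether two prescriptions belongs to the denominator or the numerator. Score these rows among all matched patients or, if two prescriptions is used as a denominator, fix that eligibility at baseline.
- **Standard rates.** Keep the unmodified CMS and PQA rates as descriptive results.

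The data are already planned: the two data sets start in 2007 and 2010 (section 5d), before the 2012 roll-out, and the date of joining HH is among the listed indicators (section 5e). The cost is some recoding and a note to Table 2. The small downside is that the effect estimates no longer match published rates one for one, which the descriptive rates cover.
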